## 4.5 Concomitant Medications and Treatments

### 4.5.1 Medications that are prohibited or used with caution during the study

#### 4.5.1.1 Prohibited medications

CFDA-approved anticancer medications are prohibited during the study, including chemotherapy agents, modern Chinese medicine preparations, and immunomodulators (such as thymosin, interferon, interleukin-2, Zilongjin, and lentinan).

#### 4.5.1.2 Medications used with caution

##### (1) Anticoagulants or antithrombotic medications:

Mainly including but not limited to salicylic acid derivatives, such as aspirin;

Heparins, such as low molecular weight heparin, enoxaparin, dalteparin, and ardeparin; Prophylactic anticoagulants after cardiovascular and cerebrovascular events, such as clopidogrel and ticagrelor.

**(2) Medications interfering with liver P450 enzymes:**

Including but not limited to CYP3A inducers (carbamazepine, rifampicin, and phenobarbital) and inhibitors (ketoconazole, itraconazole, erythromycin, and clarithromycin). The following medications should be used with caution: CYP3A4 substrates (simvastatin, cyclosporine, and pimozide); other medications metabolized by CYP3A4 (such as benzodiazepine, dihydropyridine, calcium ion antagonists (which can be selected as appropriate for hypertension that cannot be controlled by ACEIs) and HMG-COA reductase inhibitors; CYP2C9 substrates (diclofenac, phenytoin, piroxicam, S-warfarin, and tolbutamide), and CYP2C19 substrates (diazepam, imipramine, lansoprazole, and S-mephenytoin).

**(3) Medications that prolong QT interval:**

Since anlotinib has the toxic side effect of prolonging the QT interval in clinical practice, medications that can prolong the QT interval must be used with caution during the study. These medications mainly include but are not limited to:

- Antimicrobials (clarithromycin, azithromycin, erythromycin, roxithromycin, metronidazole, moxifloxacin);
- Antiarrhythmic medications (quinidine, sotalol, amiodarone, disopyramide, procainamide);
- Antipsychotics (risperidone, fluphenazine, droperidol, haloperidol, thioridazine, pimozide, olanzapine, clozapine);
- Antifungals (fluconazole, ketoconazole);
- Antimalarials (mefloquine, chloroquine);
- Antidepressants (amitriptyline, imipramine, clomipramine, dothiepin, doxepin).

**(4) Citrus, star fruit, grapefruit and grapefruit juice;**

## **4.5.2 Concomitant medications allowed during the study**

Subjects can receive supportive treatments. Supportive treatments can be combined with the following medications or related treatments: Antibiotics, analgesics, hormones, psychotherapy, or any other symptomatic treatment necessary to provide optimal supportive treatments. Other investigational antineoplastic agents or antineoplastic chemotherapy/endocrine therapy/immunotherapy are not within the scope of supportive treatment defined in the protocol.

Non-conventional treatments (e.g., herbal products or acupuncture) and vitamin/mineral supplementation are permitted if the investigator believes that they will not affect the study endpoints. Subjects may receive bisphosphonates for bone metastases during treatment.

Palliative radiation therapy involving a small area (irradiated areas must be < 5% of the marrow area) is permitted if systemic therapy or local analgesia fails to control painful bone metastases, provided that the radiation field does not include the target lesion.

During treatment, granulocyte colony-stimulating factor (G-CSF) and other hematopoietic growth factors may be used if clinical manifestations suggest or at the discretion of the investigator that treatment of acute toxicities such as febrile neutropenia is warranted. Subjects are allowed to use erythropoietin on a long-term basis.

## **4.6 Adverse Reactions and Treatment**

### **4.6.1 Hemorrhage**

VEGFR inhibitors can increase the risk of hemorrhage. Clinical studies showed that anlotinib increased the incidence of hemorrhage events compared with placebo. Therefore, clinicians should pay close attention to relevant symptoms and closely monitor the prothrombin time and international normalized ratio (INR) during dosing.

Once a grade 2 hemorrhage event is observed, treatment should be interrupted; if the severity of the event improves to < grade 2 within 2 weeks, treatment should be continued at a lower dose. Permanent discontinuation is required in case of hemorrhage events of grade 3 or higher.

Active symptomatic treatments should be provided for digestive tract hemorrhage, including fecal occult blood  $\geq ++$ , hematemesis or bloody stool. Patients with upper gastrointestinal hemorrhage should be fasted and given acid suppression agents, medications for gastric mucosa protection, hemostasis (e.g., tranexamic acid, reptilase), blood transfusion and supportive treatments. Patients with lower gastrointestinal hemorrhage should be given hemostasis, blood transfusion and supportive treatments. Patients with unmanageable hemorrhage should be treated with surgical assistance.

#### **4.6.2 Thromboembolic events**

Clinical studies showed that anlotinib may increase the risk of thromboembolic events. Thrombosis-related adverse reactions should be closely monitored during dosing, and treatment interruption is recommended if such ARs are observed. If the AR recurs after treatment resumption, discontinuation is recommended.

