### 4.4 Dose Adjustment

Adverse reactions should be closely monitored during the administration of the study drug, and the dose should be adjusted according to the patient's tolerance. Adverse reactions caused by the study drug can be treated by symptomatic treatment, drug interruption and/or dose adjustment. The dose should be adjusted under the guidance of a physician according to the severity of adverse reactions: 1) First dose adjustment: 10 mg qd for 2 weeks, followed by 1-week discontinuation; 2) Second dose adjustment: 8 mg qd for 2 weeks, followed by 1-week discontinuation. If the dose of 8 mg remains intolerable, the drug should be permanently discontinued.

Dose adjustments for each adverse reaction are as follows:

- **Hematologic Toxicities**

(1) Platelet count decreased

Grade of AE	Treatment Recommendations	Dose Adjustment
Grade 1	Perform visits as scheduled	Maintain the original dose

Grade 2	Delay dosing until AE resolves to $\leq$ grade 1	Maintain the original dose
Grade 3	Delay dosing and provide medical interventions until AE resolves to $\leq$ grade 1	Continue at a lower dose
Grade 4	Permanent discontinuation	/

(2) Neutrophil count decreased

Grade of AE	Treatment Recommendations	Dose Adjustment
Grade 1	Perform visits as scheduled	Maintain the original dose
Grade 2	Delay dosing until AE resolves to $\leq$ grade 1	Maintain the original dose
Grade 3-4	Delay dosing and provide medical interventions until AE resolves to $\leq$ grade 1	Continue at a lower dose

● **Non-Hematologic Toxicities**

(1) Hepatic function abnormal (elevated ALT, AST or TBIL)

Grade of AE	Treatment Recommendations	Dose Adjustment
Grade 1	Perform visits as scheduled	Maintain the original dose
Grade 2	Delay dosing until AE resolves to $\leq$ grade 1	Maintain the original dose
Grade 3-4	Delay dosing and provide medical interventions until AE resolves to $\leq$ grade 1	Continue at a lower dose

(2) Proteinuria

Grade of AE	Definition	Treatment Recommendations	Dose Adjustment
Grade 1	1+ proteinuria, or urine protein $<$ 1.0 g/24 h	Perform visits as scheduled	Maintain the original dose
Grade 2	2+ proteinuria, and urine protein $<$ 1.0 g/24 h	Perform visits as scheduled	Maintain the original dose
	2+ proteinuria, and urine protein is 1.0–3.4 g/24 h	Delay dosing and provide medical interventions until proteinuria $\leq$ 2+ and urine protein $<$ 1.0 g/24 h	Maintain the original dose

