#### (6) Others

Grade of AE	Treatment Recommendations	Dose Adjustment
Grade 1	Perform visits as scheduled	Maintain the original dose
Grade 2-3	Delay dosing until AE resolves to $\leq$ grade 1	Continue at a lower dose
Grade 4	Permanent discontinuation	/

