#### **4.6.4 QT interval prolongation**

Anlotinib can prolong the QT/QTc interval, which may increase the risk of ventricular tachyarrhythmias (e.g., torsades de pointes) or sudden death. Therefore, patients with congestive heart failure, electrolyte abnormality, or receiving medications known to prolong the QTc interval should undergo regular (every 3–6 weeks) electrocardiogram and electrolyte (sodium, magnesium, potassium, and calcium) tests. If the results of two consecutive independent ECG show QTc interval  $> 500$  ms, anlotinib should be interrupted until QTc interval is  $\leq 480$  ms or returns to baseline level (if QTc interval at baseline is  $> 480$  ms), then the administration can be continued at a lower dose with close ECG monitoring.

For patients with any grade of QTc prolongation ( $\geq 450$  ms) accompanied by torsades de pointes, polymorphic ventricular tachycardia, symptoms or signs of severe arrhythmia, permanent discontinuation of the study drug and specialized cardiovascular treatment are recommended.

Patients with underlying cardiac dysfunction should undergo echocardiography every 6 weeks, and discontinuation is recommended for patients with a left ventricular ejection fraction  $< 50\%$ .

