Supraventricular and nodal arrhythmias - Options: - Atrial fibrillation - Atrial flutter - Atrial tachycardia/paroxysmal atrial tachycardia - Nodal/junctional - Sinus arrhythmia - Sinus bradycardia - Sinus tachycardia	Supraventricular arrhythmia - Supraventricular premature beats (premature atrial contraction; premature contraction of atrioventricular node/atrioventricular junction area) - Supraventricular tachycardia	Asymptomatic, intervention not indicated	Non-urgent intervention indicated	Symptomatic and incompletely controlled medically, or controlled with device (e.g., pacemaker)	Life threatening (such as arrhythmia, hypotension, syncope, shock related to CHF)	Death

- Supraventricular arrhythmia NOS						
Overview of adverse cardiac events						
Left ventricular systolic dysfunction	Left ventricular systolic dysfunction	Asymptomatic, ejection fraction (EF) < 60%–50% and systolic fraction (SF) < 30%–24% at rest	Asymptomatic, EF < 50%–40% and SF < 24%–15% at rest	Symptomatic chronic heart failure, responsive to intervention, EF < 40%–20%; SF < 15%	Refractory chronic heart failure or poorly controlled, EF < 20%; intervention indicated, such as left ventricular assist device, left ventricular partial resection or heart transplant	Death
Systemic symptoms						
Tiredness (weakness, somnolence, listless)	Tiredness	Mild tiredness compared to baseline	Moderate tiredness, or causing difficulty in engaging in some activities of daily living (ADL)	Severe tiredness, limiting ADL	Causing disability	—
Fever (no neutropenia, which is defined as ANC < 1.0 × 10  /L)	Pyrexia	38.0–39.0°C (100.4–102.2°F)	>39.0–40.0°C (102.3–104.0°F)	> 40.0°C (> 104.0°F) for ≤ 24 h	> 40.0°C (> 104.0°F) for > 24 h	—
Weight loss	Weight loss	5% to < 10% decrease from baseline; intervention not indicated	10% to < 20% decrease from baseline; nutritional support indicated	≥ 20% decrease from baseline; tube feeding or total parenteral nutrition (TPN) indicated	—	—
Dermatosis/skin disorders						
Alopecia/atrichia (scalp or body)	Alopecia	Sparse or alopecia areata	Complete (bald)	—	—	—
Injection site reaction/extravasation change Other considerations: Allergic reaction/hypersensitivity (including drug fever); ulcer	Injection site reaction	Pain; pruritus; erythema	Pain or swelling with inflammation or phlebitis	Severe ulcer or necrosis; surgical treatment indicated	—	—

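### For a Grade 4 thromboembolic event, and for an LVEF below 50% graded 2 or 3 in patients with cardiac dysfunction, Protocol 4.4 and 4.6 give conflicting stop-or-resume instructions, and no rule says which governs.

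*Protocol*

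**What the plan says.** Protocol 4.4 introduces its tables with "Dose adjustments for each adverse reaction are as follows". It then covers platelets, neutrophils, liver function, proteinuria, haemorrhage, hypertension and hand-foot skin reaction, and ends with a residual table, (6) Others. No table names thromboembolism or LVEF. Under (6) Others:

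- Grade 1: "Maintain the original dose".
- Grade 2-3: hold until Grade 1 or better, then "Continue at a lower dose".
- Grade 4: "Permanent discontinuation".

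Protocol 4.6.2 gives one rule for thromboembolic events, without grades: "treatment interruption is recommended if such ARs are observed", and then "If the AR recurs after treatment resumption, discontinuation is recommended".

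The last paragraph of Protocol 4.6.4 concerns patients with pre-existing cardiac dysfunction. It asks for an echocardiogram every 6 weeks and says that "discontinuation is recommended for patients with a left ventricular ejection fraction" below 50%. Appendix III defines Grade 2 left ventricular systolic dysfunction as "Asymptomatic, EF < 50%–40% and SF < 24%–15% at rest". Grade 3 is symptomatic heart failure that responds to intervention, with EF in the band below 40% down to 20%. An EF under 20% is in Grade 4.

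Protocol 7.3.2 says that treatment stops at once for any serious adverse event. Protocol 7.2 counts life-threatening toxicity that needs hospital admission as serious.

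**The concern.** Section 4.4 presents itself as complete, so a site looking up a toxicity without its own table would reasonably use (6) Others. A site that instead turns to the toxicity text in 4.6 finds a different instruction for some grades. Nothing in the protocol ranks the two sections.

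The stake is mainly patient safety. After a life-threatening clot, or a fall in LVEF in a patient with cardiac dysfunction, whether the drug may be restarted could depend on which page was read. This is not a remote toxicity, since 4.6.2 itself says that the drug may raise thromboembolic risk.

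There is a smaller consequence for the analysis. Discontinuation for toxicity, dose intensity and time on drug would partly reflect the section used. The per-protocol set in 9.2 requires at least 2 completed cycles, so an event in cycle 1 could put a patient in or out of that set on the same basis.

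**Working it through.** The protocol states no figure on this point and no arithmetic applies. The check sets the instructions side by side by grade.

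*Thromboembolic events*

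| Grade | 4.4(6) Others | 4.6.2 (ungraded) | Result |
|---|---|---|---|
| 2-3, first event | Hold, then resume at a lower dose | Interrupt; resumption foreseen; no restart dose named | Compatible; 4.4 supplies the dose on which 4.6.2 is silent |
| 4 | Permanent stop | Interrupt; resumption foreseen; discontinue on recurrence | Conflict |

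The restart in 4.6.2 is presupposed rather than ordered: its trigger for discontinuation is a recurrence after resumption, and it makes no exception for Grade 4. If the Grade 4 event also meets 7.2, then 7.3.2 calls for immediate discontinuation and says nothing about resumption. That is a third text on the same event, not reconciled with 4.6.2.

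*LVEF in patients with pre-existing cardiac dysfunction*

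| Appendix III grade | EF band | 4.4(6) Others | 4.6.4 | Result |
|---|---|---|---|---|
| 1 | below 60% to 50% | Keep the dose | Threshold not reached | Compatible |
| 2 | below 50% to 40% | Hold, then resume at a lower dose | Discontinuation recommended | Conflict |
| 3 | below 40% to 20% | Hold, then resume at a lower dose | Discontinuation recommended | Conflict |
| 4 | below 20% | Permanent stop | Discontinuation recommended | Both stop |

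The printed Grade 2 criterion combines EF with a shortening-fraction band, and Grade 3 also refers to symptoms. The conflict therefore concerns an LVEF below 50% that actually grades as 2 or 3, and not every reading below 50%.

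*Precedence.* For a Grade 4 clot, 4.4 is the stricter text. For LVEF at Grade 2-3, 4.6.4 is the stricter. A consistent preference for either section therefore cannot be inferred from strictness. Where 4.6 means to send the reader to a table it says so, as 4.6.5 does for proteinuria; 4.6.2 and 4.6.4 refer to none.

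**The case against.** The strongest reply is that (6) Others is only a residual table, while 4.6.2 and 4.6.4 name these toxicities, so an ordinary reader would let the specific text govern. That is a fair convention, but the protocol does not state it, and the opening of 4.4 claims to cover every adverse reaction. Nor does the word 'recommended' in 4.6 rank the sections, because the middle column of the 4.4 tables is itself headed as recommendations.

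A second reply is that 4.6.2 never orders a restart after a Grade 4 clot, so a site could satisfy both texts by stopping. This stands in part. The conflict lies in what 4.6.2 permits and foresees. A site reading 4.6.2 alone would still find resumption open at every grade.

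A third reply concerns LVEF. The 4.6.4 sentence opens with patients who have cardiac dysfunction, and 3.3.10, 3.4.11 and 3.4.12 screen out many of them. It also says discontinuation without the word 'permanent', although the preceding paragraph of 4.6.4 uses that word, and the protocol elsewhere calls the scheduled week off treatment a discontinuation. These limits hold. They narrow the second conflict and show that 4.6.4 must say whether the stop is permanent, but they do not remove the mismatch with 4.4(6).

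A reader might infer more than the text supports:

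- That the sections disagree on clots at every grade. For a first Grade 2-3 event they are compatible. A Grade 1 disagreement cannot be shown, because Appendix III prints no thromboembolism row; its nearest entry, phlebitis with superficial thrombosis, has only a Grade 2 definition.
- That leaving the 6-weekly echocardiogram out of the 5.3 list is an error. Section 5.3 lists assessments for all patients, and 4.6.4 already requires this test for its subgroup.

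**Conclusion.** The protocol contradicts itself at two points: a Grade 4 thromboembolic event (4.4(6) against 4.6.2, with 7.3.2 as a third instruction if the event is serious), and an LVEF below 50% graded 2 or 3 in patients with pre-existing cardiac dysfunction (4.4(6) against 4.6.4). That is one grade of the first toxicity and two of the second.

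The conclusion rests on three readings: that toxicities without their own table belong under (6) Others; that the ungraded rule in 4.6.2 includes Grade 4; and that discontinuation in 4.6.4 means more than a hold followed by resumption at a lower dose. Because Appendix III has no thromboembolism row, the Grade 4 label for a clot has to come from the wider CTCAE.

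A reader might want to put a percentage of the 39 patients on this. The protocol gives no incidence for either event, so none is supported. No effect on the primary endpoint, DCR, is shown. The point should be corrected because it bears on patient safety and is cheap to settle. This review takes no view on which instruction is clinically right.

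**What to change.** Reconcile Protocol 4.4(6), 4.6.2, 4.6.4 and 7.3.2 so that a single instruction by grade stands for thromboembolic events and another for LVEF decrease. Within that:

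- state whether resumption is possible after a thromboembolic event, by grade, and at what dose level, so that 4.6.2 is no longer silent;
- state whether discontinuation in 4.6.4 is permanent and to which patients it applies;
- say how 7.3.2 relates to both when the event is serious;
- add cross-references between 4.4, 4.6 and 7.3.2.

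Which instruction applies, and which section prevails, is for the sponsor's medical team to decide. A cross-reference in 5.3 to the 6-weekly echocardiogram would be a convenience and is optional.

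The cost is a protocol wording amendment and a notice to sites. No additional patients or procedures are needed.

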#### **4.6.3 Increased blood pressure**

Increased blood pressure is the most common adverse reaction of VEGFR inhibitors. Previous clinical studies have shown that the incidence of hypertension events was high (about 13.61% for grade 3 or higher) in patients receiving Anlotinib Hydrochloride Capsules. Therefore, blood pressure should be measured daily for the first 6 weeks of dosing and 2–3 times a week during the subsequent dosing period.

In case of hypertension, the investigators are recommended to handle the event as follows:

- Grade 1: Prehypertension (SBP 120–139 mmHg or DBP 80–89 mmHg):  
Lack of indications for antihypertensive drugs, only blood pressure

monitoring is required;

- Grade 2: Stage I hypertension (SBP 140–159 mmHg or DBP 90–99 mmHg): Requires medical interventions; Repeated or persistent ( $\geq 24$  h), symptomatic SBP increases by  $> 20$  mmHg or increases to  $> 140/90$  mmHg compared to previous normal range; Requires monotherapy and blood pressure monitoring; Thiazide diuretics are commonly used, and angiotensin-converting enzyme inhibitors (ACEIs), angiotensin II receptor blockers (ARBs),  $\beta$ -blockers, and calcium channel blockers may also be considered;
- Grade 3: Stage II hypertension (SBP  $\geq 160$  mmHg or DBP  $\geq 100$  mmHg): Requires medical intervention; Requires multi-drug therapy, usually thiazide diuretics combined with ACEIs,  $\beta$ -blockers or calcium channel blockers;
- Grade 4: Life-threatening (e.g., malignant hypertension, transient or permanent neurologic deficit, hypertension emergency): Requires urgent intervention;

If grade 3/4 hypertension (SBP  $\geq 180$  mmHg or DBP  $\geq 110$  mmHg) is observed, anlotinib should be interrupted; If grade 3/4 hypertension is observed after anlotinib resumption, treatment should be continued at a lower dose. If grade 3/4 hypertension persists, discontinuation is recommended.

- Hypertension emergencies are defined as having DBP  $> 120$  mmHg accompanied by acute or progressive target organ damage (such as brain infarction, intracranial or subarachnoid hemorrhage, and hypertensive encephalopathy). Progressive or accelerated hypertension on the basis of chronic primary hypertension is the most common (about 40% to 50%) hypertension emergency. Treatment should be discontinued once a hypertension emergency is observed. The subject should withdraw from the clinical study and receive specialized cardiovascular treatment in time.

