#### (4) Hypertension

Grade of AE	Treatment Recommendations	Dose Adjustment
Grade 1-2	Perform visits as scheduled	Maintain the original dose
Grade 3	Delay dosing until AE resolves to $\leq$ grade 2	Continue at a lower dose
Grade 4	Permanent discontinuation	/

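### Sections 4.4 and 4.6.3 disagree on dosing after non-emergency grade 4 hypertension, and 4.6.3 ties interruption to 180/110 mmHg for a grade that it defines from 160/100

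*Protocol*

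**What the plan says.** **Section 4.4, hypertension table.** Grades 1 and 2 continue unchanged. For grade 3 the instruction is "Delay dosing until AE resolves to" grade 2 or lower, followed by a reduced dose. Grade 4 means permanent discontinuation, without qualification. The table prints no blood pressures.

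**Section 4.6.3, grade definitions.** "Grade 3: Stage II hypertension" is set at systolic 160 mmHg or above, or diastolic 100 mmHg or above. The next grade is clinical and not tied to a pressure: "Grade 4: Life-threatening (e.g., malignant hypertension, transient or permanent neurologic deficit, hypertension emergency").

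**Section 4.6.3, actions.** If grade 3/4 hypertension, with systolic 180 or above or diastolic 110 or above in brackets, "is observed, anlotinib should be interrupted". Then: "If grade 3/4 hypertension is observed after anlotinib resumption, treatment should be continued at a lower dose". Finally: "If grade 3/4 hypertension persists, discontinuation is recommended".

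**Section 4.6.3, emergency clause.** "Hypertension emergencies are defined as having DBP" above 120 mmHg together with acute or progressive target organ damage. In that case the drug is stopped and the patient leaves the study.

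**Elsewhere.** Section 7.2 counts life-threatening toxicity that needs hospitalization as a serious adverse event, and section 7.3.2 discontinues treatment immediately for such events. Appendix III, as printed, has no row for hypertension; its vascular section lists only phlebitis.

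**The concern.** Both sections tell the investigator what to do with the study drug for the same toxicity, and no sentence says which one prevails. Section 4.6.3 calls raised blood pressure the most common adverse reaction of this drug class and asks for daily readings during the first six weeks, so sites will use these rules. Section 4.6.3 is also the only place that prints the hypertension grades on which the 4.4 table depends. A site cannot apply 4.4 without opening the section that departs from it.

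At stake is whether a patient is re-exposed after an event that the protocol itself calls life-threatening, and whether sites treat the 160–179 / 100–109 mmHg range alike.

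**Working it through.** The check is mainly a comparison of the two rule sets, case by case.

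| Case | Section 4.4 | Section 4.6.3 | Result |
|---|---|---|---|
| Grade 4, emergency (diastolic >120 with organ damage) | Permanent stop | Stop and withdraw | Agree |
| Grade 4, not an emergency | Permanent stop | Interrupt; may resume; lower dose if seen again; stopping advised if it persists | Conflict |
| Grade 3 at 165/102 | Hold to grade 2 or lower, then reduce | Grade 3 by definition, but below the bracketed trigger | Inconsistent |
| First grade 3 at 182/112 | Hold, then reduce | Interrupt; restart dose not stated | Agree on the hold; restart dose unclear |
| Grade 3 again after resumption | Hold, then reduce | Lower dose | Same dose action |

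**Grade 4.** The emergency clause closes only part of the gap. Section 4.6.3 names a hypertension emergency as one of three examples of grade 4, beside malignant hypertension and neurologic deficit, so grade 4 is wider than the emergency definition. For what lies outside it, the pooled grade 3/4 wording applies, and that wording provides for resumption.

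**Threshold.** The two printed cut-offs differ by 180 − 160 = 20 mmHg systolic and 110 − 100 = 10 mmHg diastolic. For 165/102: 160 ≤ 165 < 180 and 100 ≤ 102 < 110. The reading is therefore grade 3 and below the trigger; 175/108 falls in the same band. Since 4.6.3 defines grade 4 clinically, 180/110 is not the boundary of any grade in the protocol.

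**First grade 3 event.** Section 4.4 reduces the dose after any grade 3 event. Section 4.6.3 mentions reduction only when the event is seen again. It does not give the first restart dose, so a hold followed by 10 mg satisfies both sections.

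**How many patients have the toxicity.** Inputs: "about 13.61% for grade 3 or higher" (section 4.6.3) and 39 planned patients (section 3.2). Assumption: the cited rate applies to this population.

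- Expected number: 0.1361 × 39 = 5.31.
- Binomial(39, 0.1361), 2.5th to 97.5th percentile: 2 to 10 patients.
- Chance of at least one: 1 − (1 − 0.1361)^39 = 0.997.

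These figures count patients with grade 3 or higher hypertension, not patients who meet a conflicting rule. The protocol gives no split by pressure band, by first or repeat event, or by type of grade 4 event, so that second number cannot be calculated.

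**The case against.** The strongest reply is that 4.4 is the dosing section and 4.6.3 is advice. Section 4.4 introduces its tables as the adjustments for each adverse reaction, while 4.6.3 opens its list as a recommendation to investigators. This is a natural reading, but no text states it, and section 4.6 sets binding dose rules itself. For haemorrhage, 4.6.1 requires a permanent stop at grade 3 or higher, in line with 4.4. The two sections were aligned there and not here.

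Second, non-emergency grade 4 is a narrow case. The other grade 4 examples overlap with the emergency definition, most such events would be serious adverse events, and 7.3.2 then stops treatment at once. This stands as a limit on reach. It does not remove the conflict, because 7.3.2 does not say whether the drug may be resumed. Exclusion 3.4.12, which keeps out patients with poorly controlled hypertension, may also lower the rate.

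Third, 4.6.3 does not forbid interruption below 180/110; it gives no dosing action there. A site that follows 4.4 at 165/102 breaches nothing. This is correct: the second part is an internal mismatch that invites different practice, not a pair of opposite orders. A higher hold threshold could even be deliberate, since 4.6.3 assigns multi-drug antihypertensive therapy to grade 3.

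A reader might also infer that the sections clash on recurrent grade 3, because the recurrence sentence in 4.6.3 names no hold. The documents do not support this. Both sections lead to a lower dose. The protocol uses the same wording for restarting after a hold in the 4.4 table and in sections 4.6.1 and 4.6.4, and the preceding interruption sentence in 4.6.3 is not limited to a first event.

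**Conclusion.** Two inconsistencies stand. Grade 4 hypertension outside the emergency definition is a permanent stop in 4.4 but may be resumed under 4.6.3. And 4.6.3 defines grade 3 from 160/100 while tying its interruption to 180/110. Alongside these, the restart dose after a first grade 3 event is unclear in 4.6.3. A reader might take that as a contradiction of 4.4, but a restart at the same dose is only implied, never stated.

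The traceable size is about 5 of 39 patients with grade 3 or higher hypertension, if the cited rate carries over. The number who would meet a conflicting instruction cannot be derived; for non-emergency grade 4 it is probably small. The point concerns patient safety and consistent conduct across sites. No effect on disease control rate, progression-free survival or the sample size is claimed. It should be corrected, but it does not threaten the trial's conclusion.

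**What to change.** Replace the grade 3/4 action paragraph in 4.6.3 with a reference to the 4.4 table: for grade 3, hold until grade 2 or lower and restart one dose level down; for grade 4, stop permanently. Keep the emergency clause. Delete the 180/110 bracket, so that the printed grade 3 definition of 160/100 triggers the hold. If the medical lead intends 180/110 as the hold threshold, state it in both sections instead; that choice is a medical one.

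The cost is a short amendment and a letter to sites, with no extra visits. If 160/100 is kept, there may be a few more holds and dose reductions.
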